8.1.2 Percent reduction in POS frequency

Percent reduction in POS frequency from Baseline to the On Treatment Period will be calculated as follows, where On Treatment Period Frequency is the 28-day adjusted POS frequency during On Treatment Period and Baseline Period Frequency is the 28-day adjusted POS frequency during the Baseline Period of the previous study.

$$\% \text{ Reduction} = 100 \times \frac{\text{Baseline Period Frequency} - \text{On Treatment Period Frequency}}{\text{Baseline Period Frequency}}$$

A similar calculation applies to each 3-month time interval over the On Treatment Period and for the cohort interval for each exposure duration cohort.

Percent reduction from Baseline for POS frequency will be summarized with quantitative descriptive statistics for the On Treatment Period, and by 3-month time intervals over the On Treatment Period. The summary over the On Treatment Period will include all subjects in the POS Efficacy Analysis Set. Similar summaries will be provided for the full cohort interval and by 3-month time intervals for each exposure duration cohort. Percent reduction from Baseline for POS frequency will be summarized in the same manner by geographic region.

8.1.3 Responder rate for POS frequency

Responders over the On Treatment Period are defined as subjects with a 50% or greater reduction in 28-day adjusted POS frequency from Baseline to the On Treatment Period. A similar calculation applies to each 3-month time interval over the On Treatment Period and for the cohort interval for each exposure duration cohort.

The number and percentage of responders for POS frequency will be summarized for the On Treatment Period, and by 3-month time intervals over the On Treatment Period. The summary over the On Treatment Period will include all subjects in the POS Efficacy Analysis Set. Similar summaries will be provided over the full cohort interval and by 3-month time intervals for each exposure duration cohort. Responder rates for POS frequency will be summarized in the same manner by geographic region.

8.2 Analysis of other efficacy variables

8.2.1 Subjects with partial onset seizures

All of the following variables are summarized for the Efficacy Analysis Set for POS.

8.2.1.1 Specified Month seizure freedom

The numbers and percentages of subjects who are seizure free for all seizure types for any continuous 6-month interval, 12-month interval, 18-month interval, and so forth will be summarized overall for the period of time that subjects are being treated with BRV and by

Exposure Duration Cohort. The overall summary will present the number and percentage of subjects who reported no seizures for the specified duration of seizure freedom and the seizure diary was completed for at least 90% of days within the seizure-free interval. Subjects whose duration of BRV treatment was less than the specified duration of seizure freedom will be considered failures for seizure-freedom. Summaries by exposure duration cohort will present the number and percentage of subjects who reported no seizures for the specified duration of seizure freedom at any time during the cohort interval (eg, through the end of Month 6 for the 6-month cohort) and the seizure diary was completed for at least 90% of days within the seizure-free interval. Percentages are relative to the number of subjects within each Exposure Duration Cohort.

A subject is seizure free for a 6-month interval if the subject did not report any seizures in the 6-month interval and the seizure diary was completed for at least 90% of days within the seizure-free interval. The percentage of days for which seizure diary was completed within a given 6-month interval will be calculated as follows based on a 30-day month:

$$\% \text{ of days diary was done} = 100 \times \left[\frac{180 - \text{number of days diary was not done in the interval}}{180} \right]$$

A similar calculation applies for 12-month seizure freedom based on 360 days, 18-month seizure freedom based on 540 days, and so forth.

8.2.2 Subjects with All Other Seizure Types

The following variables are summarized for the Efficacy Analysis Set for PGS.

8.2.2.1 All other type seizure days

Twenty-eight day adjusted all other type seizure days will be summarized with quantitative descriptive statistics in the same manner as 28-day adjusted POS frequency.

8.2.2.2 Percent reduction in All other type seizure days

Percent reduction in all other type seizure days from Baseline will be calculated in the same manner as percent reduction in POS frequency as described in Section 8.1.2. This variable will be summarized in the same manner as percent reduction in POS frequency.

8.2.2.3 Responder outcome for all other type seizure days

Responder outcome for all other type seizure days will be derived in a manner similar to the responder outcome for POS frequency as described in Section 8.1.3. This variable will be summarized in the same manner as 50% responder outcome for POS frequency.

8.2.2.4 Specified month seizure freedom

Specified month seizure freedom for subjects in the PGS Efficacy Analysis Set will be derived in a manner similar to specified month seizure freedom for the POS Efficacy Analysis Set as described in Section 8.2.1.1. This variable will be summarized in the same manner as specified month seizure freedom for subjects in the POS Efficacy Analysis Set.

8.2.3 QOLIE-31-P

The scoring algorithm for QOLIE-31-P is described in Section 13.1. QOLIE-31-P will be summarized for the POS and PGS Efficacy Analysis Sets. QOLIE-31-P is assessed at the following time points for subjects with POS and subjects with PGS (except for mentally impaired subjects and subjects coming from N01193): Month 2, Month 6, Month 12, Month 18, and Month 24. QOLIE-31-P is also assessed at EDVs for subjects who discontinue prior to the YEV at the end of the second year. Prior to protocol amendment 6, QOLIE-31-P may have been assessed for more than 2 years after study entry for some subjects. These additional assessments will not be summarized but will be provided in the subject data listings.

Observed values for QOLIE-31-P total score and subscale scores for Seizure Worry, Daily Activities/Social Function, Energy/Fatigue, Emotional Well-Being, Cognitive Function, Medication Effects, Overall Quality of Life, and Health Status will be summarized for Months 2, 6, 12, 18, and 24 and Last Value for the Efficacy Analysis Sets for POS and PGS. For each time point, summary statistics will be presented for the baseline scores for subjects with a change from baseline at the time point in addition to summaries of the observed values and changes from baseline at each time point. Only subjects with a non-missing change from baseline will be summarized at each time point.

For summaries of observed values at each time point, only subjects with a change from Baseline value at that time point will be summarized. Additionally, the mean and SD for each Baseline score will be provided at each post-Baseline time point for subjects included in the summary of change from Baseline.

Similar summaries will be provided for QOLIE-31-P distress items Seizure Worry, Daily Activities/Social Function, Energy/Fatigue, Emotional Well-Being, Cognitive Function, Medication Effects, and Overall Quality of Life.

The rankings of prioritization items (Seizure Worry, Daily Activities/Social Function, Energy/Fatigue, Emotional Well-Being, Cognitive Function, Medication Effects, Overall Quality of Life) will be summarized by visit for the first 2 years of the Evaluation Period, and for Last Value for the first 2 years of the Evaluation Period for the Efficacy populations for POS and PGS. Only observed values will be summarized and only the number of nonmissing values and the means for each item will be presented.

8.2.4 EQ-5D

EQ-5D (EuroQol Group, 2000) will be summarized for the POS and PGS Efficacy Analysis Sets. EQ-5D is assessed at the following time points (except for mentally impaired subjects and subjects coming from N01193): Month 2, Month 6, Month 12, Month 18, and Month 24. EQ-5D is also assessed at EDVs for subjects who discontinue prior to the YEV at the end of the second year. Prior to protocol amendment 6, EQ-5D may have been assessed for more than 2 years after study entry for some subjects. These additional assessments will not be summarized but will be provided in subject data listings.

EQ-5D dimensions will be summarized for Months 2, 6, 12, 18, and 24 and Last Value for the Efficacy Analysis Sets for POS and PGS. The number and percentage of subjects with each response will be summarized for each dimension and time point. Percentages will be relative to the number of subjects with a response to the dimension at that time point. Additionally, for each dimension and time point, the number and percentage of subjects with each response will be summarized for baseline for subjects with an observed response at that time point. Additionally, each dimension will be summarized for the 6-Month, 12-Month, 18-Month, and 24-Month Study Visit Cohorts, including summaries for baseline for all subjects within each cohort and summaries of observed responses for all time points for each cohort.

Observed values for the EQ-5D visual analog scale (VAS) score will be summarized for Months 2, 6, 12, 18, and 24 and Last Value for the Efficacy Analysis Sets for POS and PGS. For each time point, summary statistics will be presented for the baseline VAS score for subjects with a change from baseline at the time point in addition to summaries of the observed values and changes from baseline at each time point. Only subjects with a non-missing change from baseline will be summarized at each time point.

EQ-5D VAS score will also be summarized for the 6-Month, 12-Month, 18-Month, and 24-Month Study Visit Cohorts, including summaries of the baseline scores for all subjects within each study visit cohort and summaries of observed values and changes from baseline for each time point for each study visit cohort.

8.2.5 Direct cost parameters

Direct costs will be assessed based on concurrent medical procedures, healthcare provider consultations not foreseen by protocol, hospital stays, and ER visits.

Direct cost parameters will not be summarized but will be provided in subject data listings.

8.2.6 Indirect cost parameters

The number of school or working days lost will not be summarized but will be provided in subject data listings.

8.2.7 Socio-professional data

Socio-professional data are collected at the following time points: Month 12 and Month 24. Socio-professional data are also collected at EDVs for subjects who discontinue prior to the YEV at the end of the second year. These additional assessments will not be summarized but will be provided in subject data listings.

9 PHARMACOKINETICS AND PHARMACODYNAMICS

Plasma samples for BRV and concomitant AEDs and antiepileptic drugs (AEDs) will no longer be obtained. No summaries of BRV or concomitant AED/AMD plasma levels will be provided; plasma levels will only be provided in subject data listings.

10 IMMUNOLOGICAL PROCEDURES

This section is not applicable for this study.

11 SAFETY ANALYSES

Safety is assessed with AEs, laboratory tests (blood chemistry, hematology, urinalysis, and pregnancy test), vital signs, body weight, ECGs, physical examination, neurological examination, mental status, and psychiatric status. Summary tables will be provided for AEs; blood chemistry, hematology, and urinalysis; vital signs; body weight; and ECGs. No summary tables will be provided for pregnancy testing, physical examination, neurological examination, mental status, or psychiatric status.

All safety summaries will be based on the Safety Analysis Set.

11.1 Extent of exposure

A daily dose will be calculated for each study day from the day of first dose of BRV to the day of last dose of BRV for the purposes of calculating modal dose. Daily dose will be calculated as the sum of the AM and PM dose for each day.

Modal daily doses will be calculated across all study days on or after the day of first dose of BRV and up to and including the day of last dose of BRV. Modal daily dose is the most frequently taken daily dose during this period. In the event of a tie, the modal dose will be set to the lower of the tied doses. Modal daily dose will be categorized as follows:

| Category | Definition |
|-----------|--------------------------|
| 5 mg/day | <20mg/day |
| 20mg/day | ≥20mg/day to <50mg/day |
| 50mg/day | ≥50mg/day to <100mg/day |
| 100mg/day | ≥100mg/day to <150mg/day |
| 150mg/day | ≥150mg/day to <200mg/day |
| 200mg/day | ≥200mg/day |

Subject years of exposure will be calculated by summing the exposure duration in days for all subjects being summarized, and dividing the resulting value by 365.25.

Subject years of exposure will be presented overall and by modal dose for the Safety Analysis Set. The subject years of exposure presented by modal dose will be the total subject years of exposure of subjects with that modal dose.

The number and percentage of subjects exposed to BRV will be summarized overall and by modal dose category. The number and percentage of subjects in each Exposure Duration Cohort (≥3 months, ≥6 months, ≥12 months, and so forth) will be summarized.

The number and percentage of subjects within each modal dose category will be summarized for each Exposure Duration Cohort; percentages will be relative to the total number of subjects in each Exposure Duration Cohort.

In addition to the overall summaries of the above, the above will also be summarized by subgroup for region, and seizure type (Partial Onset Seizures, All Other Seizure Types).

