2 PROTOCOL SUMMARY

2.1 Study objectives

2.1.1 Primary objective

To evaluate the long-term safety and tolerability of brivaracetam (BRV) at individualized doses with a maximum of 200mg/day in subjects suffering from epilepsy

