Titration Period during which the dose of BRV is decreased in steps of 50mg/day on a weekly basis with a last down titration step at 20mg/day for 1 week. Subjects who have completed the Down-Titration Period or subjects who discontinue during the Evaluation Period without entering the Down-Titration Period enter a Post-Treatment Period for a minimum of 2 weeks and a maximum of 4 weeks and subsequently, the final visit will occur.

The maximum allowable daily dose for this study was increased from 150mg/day to 200mg/day based on amendment 6 to the protocol. It is recommended that the daily dose be administered in 2 equal intakes.

Dose adjustment to concomitant AEDs may be made at any time during the study and subjects may start new AEDs. Concomitant AEDs may also be discontinued; however, special considerations apply if the discontinuation of such AEDs results in the subject receiving BRV monotherapy. Previously, in the event of excellent efficacy and tolerability of BRV, withdrawal of concomitant AEDs resulting in monotherapy of BRV may have been attempted by the Investigator. With protocol amendment 6, conversion to monotherapy was no longer permitted; however, subjects already on BRV monotherapy are allowed to continue monotherapy treatment.

The visit schedule for this study depends on the previous study from which the subject was enrolled and the numbering of study visits differs depending on the previous study. Study visits at Months 6, 12, 18, 24, and so forth are either Full Evaluation Visits (FEVs) or Yearly Evaluation Visits (YEVs) at which a greater number of assessments are performed for all subjects from previous studies. For subjects coming from N01193, study visits at Months 1, 3, 5, 15, and 21 are minimal Evaluation Visits (MEVs) at which few assessments are generally performed. Study visits at Months 2, 4, and 9 are FEVs. For subjects coming from N01252, N01253, and N01254, study visits at Months 1, 3, 9, 15, 21 are MEVs. The study visit at Month 2 is an FEV. In addition, a phone call is scheduled at the end of the Down-Titration period and a Drug-Free Final Visit (FV) is scheduled at the end of the Post-Treatment Period. The study schedule just described is shown in [Table 2-1](#).

Table 2–1: Study Schedule

| Subjects coming from Exploratory Study (N01193) | | | Subjects coming from Confirmatory Studies (N01252, N01253, N01254) | | |
|--|-------|---------------|--|-------|---------------|

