3.2 Analysis time points

3.2.1 First and last dose of BRV

Unless otherwise noted, all references to the first dose of BRV in this SAP refer to the first dose of BRV during N01199 (ie, not the first dose of BRV from the previous study in which subjects participated in prior to N01199). Unless otherwise noted, all references to the last known dose of BRV in this SAP refer to the last dose of BRV taken across any study periods (ie, not necessarily the last dose of BRV during the Evaluation Period).

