3.2.7 Exposure duration and exposure duration cohorts

At the final analysis, the overall duration of exposure (or On Treatment Period) will be calculated as the date of last dose of BRV minus the date of first dose of BRV plus 1 day.

Each subject will be classified into one or more of the following exposure duration cohorts based on the duration of BRV exposure as calculated above:

| | |
|--------------|-----------|
| All subjects | ≥1 day |
| ≥3 months | ≥90 days |
| ≥6 months | ≥180 days |
| ≥12 months | ≥360 days |

This categorization will continue in 6-month increments past 12 months up to a time point that will be determined based on cumulative exposure at the time of the database lock.

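### Exposure by dose is tabulated only by modal dose, so the report will not show time spent on each dose, including 200 mg/day

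*SAP*

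**What the plan says.** SAP 11.1 (Extent of exposure) derives a daily dose for every day from first to last dose, and does so in order to find the modal dose. The definition is "Modal daily dose is the most frequently taken daily dose during this period". No minimum share of time is required, and in a tie "the modal dose will be set to the lower of the tied doses". The mode is then placed in one of six categories, from below 20 mg/day up to 200 mg/day and above.

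Subject-years are obtained by "summing the exposure duration in days for all subjects being summarized, and dividing the resulting value by 365.25". A subject's duration is "the date of last dose of BRV minus the date of first dose of BRV plus 1 day" (SAP 3.2.7). The last dose means "the last dose of BRV taken across any study periods" (SAP 3.2.1), so titration and down-titration days count. For the breakdown by dose, the rule is: "The subject years of exposure presented by modal dose will be the total subject years of exposure of subjects with that modal dose".

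The other dose tabulations in 11.1 (number exposed by modal dose category, and modal dose category within each exposure duration cohort) use the same classification. SAP 7 puts study drug dosing in listings. No mean-dose, maximum-dose or time-at-dose summary is planned.

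Three facts bear on the 200 mg/day row:
- SAP 2.3: "The maximum allowable daily dose for this study was increased from 150mg/day to 200mg/day based on amendment 6 to the protocol".
- Protocol Table 5:1, footnote (l): every subject had already completed the Entry Visit by the time of Amendment 6.
- SAP 2.3: planned starting doses were 20, 50 or 100 mg/day, depending on the previous study.

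**The concern.** Dosing is flexible and may continue for years, so one subject can spend long periods at several doses. The primary objective concerns safety "at individualized doses with a maximum of 200mg/day in subjects suffering from epilepsy". A natural question for a reader of the report is how much experience supports each dose level, above all the maximum that was permitted only part-way through. The modal-dose table is the only place where subject-years are broken down by dose, so it is where that reader will look. It answers a different question: how much total follow-up belongs to subjects whose most frequent dose was this one.

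The cross-tabulation with exposure duration cohorts invites the same misreading. A subject in the cohort with at least 12 months of exposure and mode 200 appears under 200 mg/day, however long or short the time at 200 was.

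**Working it through.** The documents state no exposure figure to reproduce, so the check compares the SAP rule with time at dose.

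**Formulas.** For subject i, let D(i,k) be days in dose category k, T(i) total days from first to last dose, and m(i) the category of the modal dose.
- SAP row k = sum of T(i) over subjects with m(i) = k, divided by 365.25.
- Time at dose k = sum of D(i,k) over all subjects, divided by 365.25.
- Difference = [sum over m(i) = k of (T(i) − D(i,k)) − sum over m(i) ≠ k of D(i,k)] / 365.25.

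The first term adds time spent at other doses. The second drops time at dose k in subjects with another mode. The terms have opposite signs, so the net error in a row can go either way. Over all rows the differences sum to zero, so total subject-years do not change.

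**What the documents fix.** All subjects entered under the 150 mg/day maximum, at planned doses of at most 100 mg/day. Within those limits nobody was on 200 mg/day throughout, so T(i) − D(i,200) is above zero for every subject with mode 200. A subject with up to half of all days at 200 can still add zero to the 200 row, because a tie goes to the lower dose.

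**Single-subject illustrations.** These dose histories are assumed and ignore the short starting-dose phase. Subject-years:

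| Assumed history | Row | SAP rule | Time at dose |
|---|---|---|---|
| 3 y at 150, then 4 y at 200 | 200 | 3.0 + 4.0 = 7.0 | 4.0 |
| | 150 | 0 | 3.0 |
| 4 y at 150, then 3 y at 200 | 200 | 0 | 3.0 |
| | 150 | 4.0 + 3.0 = 7.0 | 4.0 |
| Tie: 1000 days at 150, 1000 at 200 | 200 | 0 | 1000/365.25 = 2.74 |
| | 150 | 2000/365.25 = 5.48 | 2.74 |
| 400 days at 100; 200 days each at 150, 160, 170 | 100 | 1000/365.25 = 2.74 | 400/365.25 = 1.10 |
| | 150 | 0 | 600/365.25 = 1.64 |

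The last history shows a side effect of taking the mode on exact doses before grouping: a subject can be classed outside the category where most time was spent.

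**Cohort illustrations.** SAP 2.4 gives 668 enrolled. Assume 10% (66.8, taken as 67) move from 150 to 200 mg/day after Amendment 6. For the 200 row:

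| Years before / after the move | SAP rule | Time at 200 |
|---|---|---|
| 2 / 1 | 0 | 67 × 1 = 67 |
| 2 / 3 | 67 × 5 = 335 | 67 × 3 = 201 |
| 4 / 3 | 0 | 67 × 3 = 201 |
| 4 / 5 | 67 × 9 = 603 | 67 × 5 = 335 |

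The errors can also largely cancel. One simulated draw for the same 67 subjects took 1 to 5 years before the move (uniform) and exponential times after it. With means of 1, 2 and 4 years after the move, the 200 row showed 20.92 against 57.65, 167.32 against 168.92, and 297.48 against 255.83.

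**The case against.** The strongest reply is that the table cannot be wrong about something it does not claim to show. SAP 11.1 states in plain terms that the rows hold the total exposure of subjects with that modal dose, which is a legitimate way to classify subjects. That stands: there is no internal contradiction and no mislabelling.

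Nor does any planned safety estimate depend on these rows. SAP 3.1 and 3.6 present all subjects as one group, and SAP 11.2.2 breaks adverse events down by time interval, study period, region, seizure type and previous randomized treatment, never by dose. A reader might infer that dose-specific adverse event rates will be biased by these denominators. The documents do not support that, because no such rates are planned.

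The primary objective concerns a flexible regimen with a ceiling, not a separate evaluation at each dose. Overall subject-years and membership of the exposure duration cohorts serve that objective and are unaffected. Individual dosing will also be listed.

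A reader might further infer that exposure at 200 mg/day will be overstated. That is not established either: the date of Amendment 6, the number of subjects reaching 200 mg/day and their dose histories are not given.

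Finally, simply summing days by the existing categories would create a new problem. Exposure duration makes no deduction for gaps, and the lowest category is everything below 20 mg/day, so days without drug would appear as low-dose exposure. That objection is sound, and the fix must deal with it.

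What remains is that correct labelling does not supply the missing quantity. Listings for several hundred subjects are not a usable substitute for a summary of time at each dose.

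**Conclusion.** The point holds as a low-cost improvement to a descriptive summary, not as an error in the plan. The modal-dose table does not measure time on each dose, and nothing else tabulated does. For subjects treated within protocol limits, the 200 mg/day row will always include time at lower doses from those with mode 200, and will always leave out the time at 200 of those with another mode or a tie. This rests on the Entry Visit footnote, the planned starting doses and the earlier 150 mg/day maximum.

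The net direction and size cannot be known from the documents. Under the assumed cohort histories the 200 row ran from 0 against 201 to 603 against 335, with near-agreement also possible. These figures show what the rule can do and do not predict what the report will show.

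**What to change.** In SAP 11.1:

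1. Add one table of subject-years by actual daily-dose category: days in each category summed over all subjects, divided by 365.25. Use the existing dose categories.
2. Show days with a zero or missing dose in a separate row, outside the lowest category, so that the rows still add to total subject-years. Identify down-titration days so that they are not read as chosen maintenance exposure.
3. For each category, give the number of subjects ever exposed and the number cumulatively exposed for at least 6 and 12 months (180 and 360 days, following the 30-day month in SAP 3.2.5). State that these durations are cumulative, not continuous.
4. Keep the modal-dose tables to classify subjects, with a footnote that their subject-years are not time at that dose.

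The cost is one extra table and a written rule for zero-dose and missing-dose days. The daily doses are already to be derived, so no new data and no change to study conduct are needed.
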